While each included patient’s data will be recorded retrospectively after randomization, we do believe that it is necessary to perform this study in a prospective manner rather than fully retrospective. It is not feasible to perform this study retrospectively as we would not be able to ensure adequate and equal numbers in each group within the medical critical care unit, especially considering how medical critical care patients are placed in other intensive care units within our institution based on bed availability. Unequal groups would unduly bias the results and make the analysis less meaningful in terms of contributing to the current body of evidence.

Any medication events, including adverse drug reactions or medication errors, will be routinely reported throughout the study to the UTMC Safety Intelligence system. Routine reports of events related to the study will be reviewed weekly by our medication safety office if necessary. Data will be collected continuously throughout the study duration and investigators will review the data for any concerning safety or efficacy differences between the treatment groups. Upon regular screening for adverse drug events, if any are detected, they will be not only be reported to the Safety Intelligence system but will also be reported for review by the IRB.

Per the FDA guidance for clinical investigators regarding the need for an investigational new drug (IND) application in human research studies, investigations are exempt if the drug is lawfully marketed in the U.S., the investigation is not intended to support a new indication or change the labeling of the drug, the investigation will not support a change in advertising for the drug, and the route of administration, dose, or any other factor of the investigation will not increase the risk associated with the drug⁷. Our study, since we are not changing standard of care and are using accepted, studied doses of hydrocortisone and fludrocortisone, meet these criteria for exemption from IND application.

Outcomes:

- Primary Endpoint:
 - Time to resolution of shock (defined as 24 hours vasopressor free)
- Secondary Endpoints:
 - ICU Length of Stay (LOS)
 - Hospital LOS
 - All-cause mortality at ICU discharge
 - All-cause mortality at hospital discharge
 - All-cause mortality at 28 days of admission
 - All-cause mortality at 90 days of admission
 - Withdrawal of treatment therapy during ICU stay

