- Continuation of baseline/prior steroid in combination with hydrocortisone/fludrocortisone
- Inhaled corticosteroid use
- Intubation with etomidate
- Amount of diuretics received during study period
- Acute respiratory distress syndrome documented during study period
- Administration of neuromuscular blocker during study period

Statistical Analysis:

Statistical Power

In order to achieve adequate statistical power for the proposed prospective trial, an a priori sample size calculation was completed based on an evidence-based measure of effect size from the APROCCHSS and CORTICUS trials^{3,4}. The evidence-based difference between the treatment groups was 24 hours (Group 1 $M = 96$, $SD = 36$; Group 2 $M = 72$, $SD = 36$), leading to a Cohen's d effect size of 0.67. With a two-tailed hypothesis, an effect size of $d = 0.67$, an alpha value of 0.05, and equal allocation to treatment groups (1:1), 39 participants would be needed for each treatment group. This means the total sample size will be $n = 78$ in order to achieve adequate statistical power for the trial.

Statistical methods

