Frequency and percentage statistics will be used to analyze categorical demographic, predictor, confounding, and outcome variables of interest for the sample. Descriptive statistics will be used to describe the sample characteristics associated with continuous variables. The assumption of normality of continuous distributions will be assessed using skewness and kurtosis statistics. If either statistic is above an absolute value of 2.0, then the distribution will be assumed to be non-normal. Homogeneity of variance between independent groups will be tested using Levene's Test for Equality of Variances. When both statistical assumptions are met, independent samples t-tests will be used to compare the treatment groups on continuous outcomes. Means and standard deviations will be reported and interpreted for these analyses. Mann-Whitney U tests will be used for comparisons when statistical assumptions are violated. Medians and interquartile ranges will be presented and analyzed for non-parametric comparisons. Chi-square tests will be used to test for significant associations between the treatment groups and categorical outcomes. Relative risk with 95% confidence intervals will be reported for significant categorical associations. Multiple regression analysis will be performed with time to resolution of shock as the outcome. Linearity, normality, homoscedasticity, multicollinearity, and autocorrelation assumptions for the regression analysis will be performed. Unstandardized beta coefficients, standard errors of the coefficients, and standardized beta coefficients will be reported and interpreted, along with the change in shared variance (R^2) and respective F-tests. All analyses will be conducted using SPSS Version 22 (Armonk, NY: IBM Corporation) and statistical significance will be assumed at an alpha value of 0.05.

A priori subanalysis will be performed on the following subset of patients: documented history of heart failure and documented chronic kidney disease stage III and IV requiring renal replacement therapy at baseline.

Critical Analysis/Limitations:

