Limitations of this study will include the open-label design without blinding and placebo controls. Also, as data collection will be retrospective in nature, we will be relying on nursing documentation for timing of vasopressor initiation and discontinuation for our primary outcome. This could introduce documentation bias, but it is important to point out that our critical care nursing staff document pressor requirements hourly. Also, to note, previous trials have utilized fludrocortisone 50 mcg doses. Currently, the only commercially available fludrocortisone product in the United States is a 100 mcg tablet. In order to comply with the

previously studied dose and the current guideline recommended therapy, we will be utilizing fludrocortisone 50 mcg in our study. This will be achieved by splitting the available 100 mcg tablet in half. Education will be provided to all providers, pharmacists, and nursing involved in the project about the correct dose for fludrocortisone and the appropriate way to order the dose.

Protected Health Information:

Patients and their specific health information will be de-identified to protect privacy. Any information collected that contains PHI will be stored in a secure, locked area on password-protected electronic files that are only accessible to study investigators. Any information containing PHI will be properly disposed of at the end of the study period.

Study Budget: Cost of printing of notification of research

Timeline:

Estimated October 2018 through July 2019

References:

1. Long B and Koyfman A. Controversies in corticosteroid use for sepsis. *J Emerg Med.* 2017; 53 (5): 653-661.

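### The primary endpoint has no value for a patient who dies before 24 vasopressor-free hours, and the planned tests have no rule for that patient, so the comparison is restricted to resolvers

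*Combined protocol and SAP*

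**What the plan says.** - Outcomes, Primary Endpoint: "Time to resolution of shock (defined as 24 hours vasopressor free"). The Objective uses the same definition. Neither says that the patient must be alive.
- Statistical methods: when normality and equal variance hold, "independent samples t-tests will be used to compare the treatment groups on continuous outcomes"; otherwise "Mann-Whitney U tests will be used for comparisons when statistical assumptions are violated". In addition, "Multiple regression analysis will be performed with time to resolution of shock as the outcome".
- Statistical Power: means of 96 and 72 h, SD 36, two-sided alpha 0.05, and "39 participants would be needed for each treatment group", 78 in total. No power target is given, and no allowance for patients without a value is stated.
- Outcomes, Secondary Endpoints: deaths are expected and counted separately, beginning with "All-cause mortality at ICU discharge".
- Critical Analysis/Limitations: the investigators will be "relying on nursing documentation for timing of vasopressor initiation and discontinuation for our primary outcome". This implies, without confirming, that the clock starts at vasopressor initiation. No end of follow-up is set.

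No section gives a censoring rule, a competing-event rule, an assigned value or rank, or a missing-data rule for a patient who never resolves.

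**The concern.** Time to resolution is a time-to-event outcome, and death prevents the event. A t-test, a Mann-Whitney test and a linear regression each need a number for every patient, so a patient without one falls out. The primary comparison is then made among survivors to resolution, a group formed after assignment and possibly influenced by treatment. The Background itself treats a mortality difference between the two regimens as an open question.

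The handling is also left to be settled later. The trial is open-label, data are collected retrospectively from charts, and the Protocol section has the investigators looking at efficacy differences between the arms while the study runs. A rule written at the analysis stage would be written with outcomes visible.

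**Working it through.** **1. The plan's own figure.** Inputs from Statistical Power: d = 24/36 = 0.667, two-sided alpha 0.05. Power is not stated; 80% is assumed here.
- Normal approximation: n = 2(1.960 + 0.842)²/0.667² = 35.3, so 36 per arm.
- t-test (noncentral t): 36.3, so 37 per arm.
- Mann-Whitney (t-test n divided by its efficiency of 0.955): 36.31/0.955 = 38.02, so 39 per arm, which matches the plan.

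On the Mann-Whitney reading nothing is spare. On the t-test reading 39 − 37 = 2 per arm are spare, about 5%.

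**2. Power if unresolved patients are dropped.** With unresolved share m unrelated to speed, the evaluable number per arm is 39(1 − m). Two-sided t-test, d = 24/36:

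| m | Evaluable per arm | Power |
|---|---|---|
| 0 | 39 | 83% |
| 10% | 35.1 | 79% |
| 20% | 31.2 | 74% |
| 30% | 27.3 | 68% |

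If slow patients are likelier to die (correlation 0.5), simulated power is 83, 82 and 79% at 10, 20 and 30% unresolved, against a simulated 81% with no deaths. The loss is then slight or absent.

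**3. Bias among resolvers.** Simulation: 39 per arm, 3,000 trials per scenario, gamma resolution times with SD 36 h. All death rates are assumptions. In model (i) a stated share is destined to die, with exponential death times of mean 72 h, and resolves only if resolution comes first. In model (ii) a stated share never resolves. Death is independent of resolution time or linked to it (correlation 0.5 or 0.8). There is no true effect on speed.

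| Death risk by arm | Model (i), correlation 0 to 0.8 | Model (ii), correlation 0.8 |
|---|---|---|
| 30% v 30% | 0 h; 5-6% false positives | not needed |
| 30% v 40% | 0.8-2.5 h; 5-6% | 4.0 h; 9% |
| 30% v 55% (extreme) | 2.3-5.5 h; 5-11% | 9.6 h; 23% |

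The more lethal arm looks faster.

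**4. Dependence on the unwritten rule.** Model (i), 30% death risk in both arms. Three handlings: drop the patient, enter the time at which vasopressors stopped at death, or rank the patient worst.
- True 24 h effect: power about 75-77%, 56% and 61-64% respectively.
- No effect: each rule alone rejects about 5%, but at least one of the three rejects in 11-13% of trials, about 12%.

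**5. Power of the alternatives.** Model (i), independent deaths, true 24 h effect, both arms alike:

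| Death risk (share unresolved) | Resolvers-only t-test | Cause-specific log-rank | Worst rank | Gray-type |
|---|---|---|---|---|
| 10% (6%) | 79% | 67% | 79% | 50% |
| 20% (13%) | 77% | 65% | 71% | 41% |
| 30% (19%) | 75% | 64% | 62% | 33% |
| 40% (26%) | 73% | 62% | 54% | 29% |

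With no deaths the log-rank already has 68% against 81% for the t-test, so most of the gap comes from the change of test and not from the deaths.

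**6. Rejection on mortality alone.** No speed effect, model (i), at 30% v 40% and then 30% v 55%: cause-specific log-rank 5-6%, then 5-7%; worst rank 6-7%, then 17-23%; Gray-type 9-10%, then 28-34%. The cause-specific test is not immune: if 30% v 55% never resolve (model ii), it rejects in 20% of trials, against 51% for worst rank and 59% for Gray-type.

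**The case against.** **The harm shown is modest.** A resolvers-only comparison keeps its error rate when mortality is equal and nearly keeps it at 30% v 40% under model (i). The documents supply no death rate. This stands. A reader might infer that the primary result will be seriously biased; the documents do not support that, because nothing in them says that mortality will differ between the arms.

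**The sample size may contain slack.** A reader might infer that 78 was fixed with no margin. With no power target stated, the t-test reading leaves two patients per arm. Only the absence of a stated allowance can be asserted; two per arm would not cover even 10% unresolved.

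**Counting a death as resolution is strained.** The definition asks for 24 vasopressor-free hours, and a patient who dies as vasopressors stop has no such observed period. It would be wrong to say that the plan intends this. The wording merely fails to exclude it.

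**A competing-event or worst-rank primary test is costly and answers another question.** Both can reject on mortality alone, and the Gray-type test has about 33% power at 30% death risk. This stands. The Objective concerns speed, which the cause-specific log-rank fits better.

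**A new method would still not analyse everyone allocated.** Inclusion in the combination group requires fludrocortisone within 24 h of hydrocortisone. Read literally, a patient who dies before the first dose leaves that arm only. With no treatment effect, equal death risk of 30 or 50%, and first dose assumed uniform over 0-24 h, worst rank rejects about 6-7% and Gray-type 7-8%, while resolvers-only stays at 5%. The distortion is modest, but it bars any claim that all allocated patients are analysed.

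The endpoint "Withdrawal of treatment therapy during ICU stay" is also undefined. That is a separate gap and no part of this point.

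**Conclusion.** The point holds and should be settled before analysis. The primary endpoint does not exist for a foreseeable group of patients, and the named methods suit complete continuous data, not a time-to-event outcome cut short by death. Followed literally, the plan compares resolvers only.

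The main defect is the method and the missing rule, not a demonstrated large bias. Under assumed death rates the bias is nil at equal mortality and about 1-4 h, with 5-9% false positives, at 30% v 40%. It becomes material only if mortality differs widely. A free choice among three plausible rules raises the false-positive rate to about 12% at equal 30% death risk. Power of 83% falls to 79, 74 or 68% at 10, 20 or 30% unresolved if deaths are unrelated to speed, and by less if slow patients are likelier to die. These figures rest on the plan's 24 h difference and SD of 36 h and on assumed death rates. The simulated ones also depend on the assumed gamma times and death models.

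**What to change.** 1. In Outcomes, define resolution as alive and vasopressor-free for 24 h. State time zero and a fixed horizon, such as day 28.
2. In Statistical methods, before analysis, replace the t-test, the Mann-Whitney test and the linear regression for the primary endpoint with a time-to-event analysis of every included patient. Use a cause-specific log-rank test and Cox model, in which death before resolution ends follow-up, as the comparison of speed. Beside it show the cumulative incidence of resolution with death as a competing event, and the number of deaths before resolution by arm. Keep resolver-only times as description. A worst-rank Mann-Whitney or a Gray test is acceptable if declared as mixing mortality and speed.
3. In Statistical Power, restate the power of n = 78 under the chosen method as a range over the unresolved share.
4. Reconcile the analysis set with the 24-hour fludrocortisone inclusion criterion. Otherwise do not claim that all allocated patients are analysed.

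**Cost.** Mostly wording. Vasopressors are charted hourly, and length of stay with mortality at each discharge dates in-hospital deaths, so little new data is needed. Confirm that the named SPSS version runs the chosen methods, or name another program. Power is lower: about 67, 65, 64 and 62% at 10, 20, 30 and 40% death risk, against 79, 77, 75 and 73% for the resolvers-only t-test. The effect is no longer in mean hours. The case for the change is validity, not power.

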 - Reinitiation of vasopressor therapy (after vasopressor free for 24 hours)
 - Reinitiation of hydrocortisone and/or fludrocortisone
 - Mechanical ventilator free days during ICU admission
 - Duration of steroid therapy
- Safety Endpoints
 - Documentation of two consecutive point of care blood glucose checks >180 mg/dl after initiation of hydrocortisone and/or hydrocortisone/fludrocortisone
 - Gastrointestinal bleed during study period (as documented by provider)
 - Severity of bleed as determined by GUSTO criteria
 - Severe: deadly bleeding; intracerebral bleeding or substantial hemodynamic compromise
 - Moderate: bleeding requiring transfusion
 - Mild: other bleeding not requiring transfusion or causing hemodynamic compromise
 - New initiation of renal replacement therapy during study period
 - Electrolyte abnormalities
 - Sodium level greater than 150 mEq/L during study period
 - Potassium level greater than 5.5 mEq/L during study period

Other Data Collected:

- Demographics: Age, sex, weight, height, BMI, ethnicity (race)
- Septic Shock Bundle initiated
- WBC at time of steroid initiation and at discontinuation

- Initial lactic acid level on admission
- Lactic acid level at initiation of vasopressors
- Vasopressor initiated (norepinephrine, epinephrine, phenylephrine, vasopressin, dopamine, dobutamine)
- Vasopressor dose when steroid therapy was initiated (mcg/min and mcg/kg/min)
- Max vasopressor dose during study period
- SOFA Score
- APACHE Score
- Charlson Comorbidity Index
- Site of infection (lung, intraabdominal, urogenital, skin, CNS, endocarditis, bacteremia, unknown, etc.)
- Non-contaminant, positive culture during study period with clinical correlation to septic shock event
 - Site of culture
 - Gram Positive
 - Gram Negative
 - Viral
 - Fungal
 - Organism
- Comorbidities:
 - Documented heart failure
 - Documented chronic kidney disease stage III-IV not requiring renal replacement therapy at baseline
- Documentation of concurrent cardiogenic shock during study period
- Serum creatinine at initiation of steroid therapy
- Serum creatinine at discontinuation of steroid therapy
- Renal replacement therapy at the initiation of steroid therapy
- Mechanical ventilation at initiation of steroid therapy
- Other systemic steroid use (methylprednisolone, dexamethasone, prednisone) prior to pressor initiation
- Systemic steroid use prior to admission (home medication)

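### Eleven secondary outcomes are tested at an unadjusted 0.05 with no exploratory label, and relative risks are promised only for the significant ones

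*Combined protocol and SAP*

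**What the plan says.** The Outcomes section of the combined protocol and SAP names one primary endpoint, "Time to resolution of shock (defined as 24 hours vasopressor free"), then 11 secondary endpoints and a list of safety endpoints.

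- **Secondary, categorical (7):** all-cause mortality at ICU discharge, at hospital discharge, at 28 days ("All-cause mortality at 28 days of admission") and at 90 days; withdrawal of treatment; restart of vasopressors; restart of steroids.
- **Secondary, continuous (4):** ICU stay, hospital stay, ventilator-free days, steroid duration.
- **Safety (6, or 5 if bleed grading is not a separate test):** raised glucose, gastrointestinal bleed, its grading ("Severity of bleed as determined by GUSTO criteria"), new renal replacement therapy, high sodium, high potassium.

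Under Statistical methods, continuous outcomes get a t-test or Mann-Whitney test and categorical outcomes get a chi-square test, with no restriction to particular endpoints. For all analyses, "statistical significance will be assumed at an alpha value of 0.05". Relative risks with 95% confidence intervals are promised for significant categorical associations only. For continuous outcomes the plan gives group summaries (mean and SD, or median and interquartile range) and does not mention a difference with an interval.

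No section gives a multiplicity adjustment or a testing order, or says how secondary p-values are to be read.

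**The concern.** Two features act together. Many secondary outcomes are tested at the level used for the primary, so some chance of a spurious positive is built in. The reporting rule then makes the p-value decide which categorical outcomes receive an effect estimate. A chance finding would appear with a relative risk and interval, while null outcomes would appear with a p-value and percentages.

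Mortality is where this could mislead most. The Background presents the effect of steroids on mortality as the controversial question, but the sample size rests on a difference in hours. With about 39 patients per arm, a mortality comparison reaches p < 0.05 only when the observed gap is large. Any mortality relative risk that passes the filter will therefore look striking, and readers would lack the estimates for the other time points that put it in context.

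**Working it through.** **1. The plan's own figure.** The plan states no familywise error rate, so there is none to reproduce. Its one calculation is the sample size: "The evidence-based difference between the treatment groups was 24 hours", SD 36, so d = 24/36 = 0.667, two-sided 0.05, and "39 participants would be needed for each treatment group". Power is not given as a number. Assuming 80%, a t-test needs 37 per group, and allowing for Mann-Whitney efficiency (3/π) gives 39. The figure can thus be reproduced. It matters here only because a 24-hour difference fits the primary endpoint and none of the mortality endpoints.

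**2. Inputs.**
- From the plan: 0.05 per test; k = 11 secondary outcomes (7 + 4), of which 4 are mortality.
- Assumed: no true effect on any of them, and a common correlation ρ between test statistics. The documents give no correlations, so a range is shown.

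**3. Formulas.** With independent tests, P(at least one p < 0.05) = 1 − 0.95^k. With common correlation ρ, P = 1 − ∫ φ(u) [Φ((1.96 − √ρ·u)/√(1−ρ)) − Φ((−1.96 − √ρ·u)/√(1−ρ))]^k du.

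**4. All 11 secondary outcomes.**

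| Assumed ρ | P(at least one p < 0.05) |
|---|---|
| 0 | 1 − 0.95^11 = 43% |
| 0.3 | 37% |
| 0.5 | 30% |
| 0.7 | 22% |

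The expected number of false positives is 11 × 0.05 = 0.55, whatever the correlation.

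**5. The four mortality outcomes.** Deaths by one time point are largely the same deaths counted at the next, so high correlation is the realistic end.

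| Assumed ρ | P(at least one p < 0.05) |
|---|---|
| 0 | 1 − 0.95^4 = 19% |
| 0.8 | 11% |
| 0.9 | 9% |

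Even with heavy overlap, this is roughly double the nominal 5%.

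**6. Size of effect that passes the filter.** Take an illustrative 18 deaths among 39 in one arm (46%, an assumption), and use the chi-square test without continuity correction.
- Against 9 of 39: gap 9/39 = 23.1 points; pooled rate 27/78 = 0.346; SE = √(0.346 × 0.654 × 2/39) = 0.108; z = 2.14, significant.
- Against 10 of 39: gap 8/39 = 20.5 points; pooled rate 28/78 = 0.359; SE = 0.109; z = 1.89, not significant.

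For assumed mortality of 30% to 60% in the higher arm, the required gap is about 20 to 23 points. The mortality relative risks that the plan commits to report are those with gaps of about that size or more.

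**The case against.** A fair defence is that one primary endpoint is named, the Objective mentions only resolution of shock, the regression has only the primary as its outcome, and the sample size fits only the primary. Leaving secondary outcomes unadjusted under a single primary is common and defensible in a small single-centre comparison of two regimens described as standard of care. That stands, and it rules out three stronger readings.

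- *That the trial has no hierarchy, or that a mortality p-value ranks equally with the primary.* A reader might infer this from the uniform 0.05. The documents do not say it: they separate primary, secondary and safety endpoints. What they lack is a testing order or an exploratory label.
- *That the main conclusion is at risk.* Testing other outcomes does not raise the error rate of the single primary comparison.
- *That a false positive is about as likely as not.* Counting all 17 non-primary outcomes gives 1 − 0.95^17 = 58% under independence. That count includes six safety comparisons, which should stay unadjusted so that harm signals are not hidden, and it treats bleed grading as a test of its own. It also falls to 39% at ρ = 0.5 and 27% at ρ = 0.7. It is not the right measure of the problem.

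A continuity-corrected chi-square would lower the rates further; the plan does not say which form will be used. Holm adjustment, or choosing one mortality time point as the main one, would be a trade-off for the investigators and is not required by anything the plan claims.

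The defence does not answer the reporting rule. Unadjusted secondary tests are acceptable when labelled exploratory and reported in full. This plan does neither.

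**Conclusion.** The point holds in a limited form. The plan tests 11 secondary outcomes at an unadjusted 0.05, gives no guidance on how to read them, and lets significance decide which categorical outcomes are promised an effect estimate. With no true effects, the chance of at least one nominally significant secondary result is about 30% to 43% (ρ from 0.5 to 0), and of at least one nominally significant mortality result about 9% to 19% (ρ from 0.9 to 0). These figures rest on all the relevant null hypotheses being true and on assumed correlations; stronger correlation gives lower values. The reporting rule is in the text and depends on no assumption. The primary analysis is unaffected. This is a cheap improvement, not a flaw that threatens the trial.

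**What to change.** In Statistical methods:

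1. Limit the 0.05 significance rule to the primary endpoint.
2. Replace the sentence on relative risks with a commitment to report every secondary and safety outcome, whatever its p-value, with an effect estimate and 95% confidence interval: relative risk or risk difference for categorical outcomes, mean or median difference for continuous ones.
3. Label secondary outcomes exploratory and safety outcomes descriptive.

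This needs no extra patients or data, only a few sentences and slightly longer results tables. The cost is that no secondary result, mortality included, can be claimed as significant on its unadjusted p-value.

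### The planned heart-failure and kidney subanalysis has no contrast with the remaining patients; a test inside the subset cannot show whether the effect differs there

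*Combined protocol and SAP*

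**What the plan says.** The last paragraph of Statistical methods states: "A priori subanalysis will be performed on the following subset of patients: documented history of heart failure". The sentence then adds chronic kidney disease stage III and IV with renal replacement therapy at baseline. It gives no outcome, test, sample size or rule of interpretation for this subanalysis, and no comparison with patients outside the subset.

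The two-group tests named in the same section are the t-test, Mann-Whitney U and chi-square. For all analyses, "statistical significance will be assumed at an alpha value of 0.05". The section also says "Multiple regression analysis will be performed with time to resolution of shock as the outcome", but it lists no predictors, so an interaction term is neither planned nor excluded.

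Statistical Power sizes the trial for the overall comparison only: "39 participants would be needed for each treatment group", 78 in total. Documented heart failure appears under Other Data Collected as a comorbidity. No expected share of patients with it is given.

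**The concern.** One main reason to single out a subset in advance is to learn whether the treatment effect differs there. That question needs a contrast between the effect inside the subset and the effect outside it. A p-value from inside the subset alone does not supply this contrast, because it depends heavily on how many patients the subset contains.

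If the two-arm test is simply repeated in a small part of a 78-patient trial, the probable result under a benefit common to everyone is a significant trial with a non-significant subset. That pattern invites a reader to conclude that adding fludrocortisone does not help in heart failure, when the data may be fully consistent with the same effect.

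**Working it through.** **Inputs from the Statistical Power section.** "Group 1 $M = 96$, $SD = 36$; Group 2 $M = 72$, $SD = 36", so the difference is 24 h and d = 24/36 = 0.667. "With a two-tailed hypothesis, an effect size of $d = 0.67$, an alpha value of 0.05". Allocation is 1:1 with 39 per arm.

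**Assumptions.** The plan gives no numerical power; 80% is assumed to reproduce its sample size. The heart-failure share is not given and is varied. Time to resolution is treated as a fully observed continuous outcome, as the plan's own calculation does. Allocation by unit location is ignored.

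**The plan's figure.** The normal formula gives n per arm = 2(1.960 + 0.842)² / 0.667² = 35.3, hence 36. The exact t-test needs 37. Allowing for Mann-Whitney efficiency 3/π gives 37/0.955 = 38.7, hence 39, which matches the plan. At 39 per arm the t-test has 83% power.

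**Power inside the subset.** With n heart-failure patients per arm, the standard error is 36√(2/n). Power comes from the noncentral t distribution with noncentrality 24/SE and 2n − 2 degrees of freedom. At n = 10, SE = 36√0.2 = 16.1 h and noncentrality = 1.49; the critical t is 2.10, so the 95% CI half-width is 2.10 × 16.1 = 34 h.

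| Heart failure per arm | Share of 78 | Subset power | 95% CI half-width |
|---|---|---|---|
| 8 | 21% | 24% | 39 h |
| 10 | 26% | 29% | 34 h |
| 12 | 31% | 35% | 30 h |
| 20 | 51% | 54% | 23 h |

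Power reaches 50% at 18.3 per arm, that is 36.6/78 = 47% of patients. Below that share, the subset test misses a uniform 24 h benefit more often than it detects it.

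**Given a significant overall result.** In 40,000 simulated trials per setting with a uniform 24 h effect, the subset was still non-significant in 73%, 66%, 60% and 37% of the overall-significant trials at 8, 10, 12 and 20 per arm.

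**The interaction alternative.** With 10 heart-failure patients and 29 others per arm, SE = 36√(2/10 + 2/29) = 18.7 h. With 74 degrees of freedom the 95% CI half-width is 1.99 × 18.7 = 37 h. Under a uniform effect the interaction test signals a difference in 5% of simulated trials. If the benefit is 24 h without heart failure and 0 h with it, its power is about 25% at 10 per arm, and 14% to 31% over shares of 10% to 50%.

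**No effect anywhere, 10 per arm.** The subset test is significant with a non-significant overall test in 4.2% of trials; for the interaction test the figure is 4.7%.

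**The case against.** The strongest reply is that the plan never says it will test inside the subset. It announces a subanalysis and stops there; the regression's predictors are unlisted, and neither the Objective nor the Outcomes asks whether the effect differs in heart failure. This stands as a limit on the wording: within-subset testing is the natural reading, not stated text. It does not remove the point, because no contrast with the other patients appears anywhere, and someone following the section as written would have only the two-arm tests to apply.

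A second reply is that the sentence refers to a single subset and joins heart failure and kidney disease with *and*, so it may mean patients with both. That also stands. A joint subset could be no larger than the heart-failure group, so power would be no better, but the figures above would not describe it directly.

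A third reply is that the interaction test is itself weak at this size, and that its non-significance could be misread as proof of equal effects. This is correct, and it is why the estimate and its CI should be reported rather than a verdict.

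Two stronger readings are tempting. A reader might infer that the sponsor intends to declare the combination ineffective in heart failure; no sentence plans such a conclusion. A reader might also infer that an interaction test protects against chance findings in a null trial. It does not: 4.7% against 4.2% is no improvement.

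**Conclusion.** The point holds in this form: the plan provides no contrast between the subset and the remaining patients, and its most natural reading yields a p-value that cannot show a different effect. At 8 to 12 heart-failure patients per arm, that test would miss a uniform benefit in about 65% to 76% of trials.

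A reader might infer that a uniform benefit will usually look absent in heart failure whatever the case mix. The documents do not support that without a condition, since they give no heart-failure share: the miss rate exceeds one half only below about 47%, and at 20 per arm it is 46%. The figures also assume that the subanalysis concerns time to resolution of shock, that heart failure is a subset in its own right, and that the plan's 24 h and 36 h are right. The overall primary comparison is unaffected.

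**What to change.** First settle the definition. State whether the sentence means one joint subset or two separate ones. Reconcile the kidney criterion as well: Other Data Collected records chronic kidney disease without renal replacement therapy at baseline, whereas Statistical methods names a subset with it.

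Then replace the subset analysis with the following:

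- Keep all 78 patients in the model.
- Add arm by heart failure to the planned regression, with both main effects, or the equivalent term in whatever primary model is finally used. If a joint subset is meant, use membership of that subset instead.
- Report the treatment effect with a 95% CI in patients with and without heart failure, and the interaction estimate with its 95% CI.
- Label the analysis exploratory. State that no subgroup claim will rest on a within-subset p-value, and that a non-significant interaction will not be read as equal effects.
- Treat the kidney subset in the same way once it is defined.

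The cost is one model term and a few sentences. Heart failure is already collected, so no further patients or data are needed and clinical care does not change. The price is visible imprecision in the interaction estimate, and the change does not lower the roughly 4% to 5% rate of chance-positive signals when there is no effect.
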